Overview of General Design

We will utilize a randomized, double-blind, parallel-groups design. After pre-treatment assessment to confirm SUD diagnosis and characterize baseline level of use and functioning, subjects will be randomized (by computer algorithm) to either the active or sham rTMS arms. They will then receive rTMS or sham in the 2-week treatment phase, at the end of which subjects will repeat assessments to determine immediate post-treatment relapse status. In the follow-up period (3- months post treatment), we will determine the longer-term effects of rTMS by obtaining relapse status and level of functioning, along with secondary outcome measures described below.

Subjects, Screening Procedures and Randomization

General characteristics, including sex, race and ethnic origin of subjects to be recruited. Subjects with SUD between the ages of 18 and 65 will be studied. The study will be open to both men and women, regardless of race and ethnic origin.

Exclusion Criteria	Inclusion Criteria
1) Pregnant or lactating female	1) Age 18-65 years
2) History of prior adverse reaction to TMS	2) SCID confirmed diagnosis of SUD
 On medications thought to significantly lower seizure threshold, e.g. clozapine, chlorpromazine, clomipramine, and bupropion > 400mg/day 	3) Last use of stimulants > 2 and < 8 weeks
4) Seizure disorder or conditions known to substantially increase risk for seizures	 Stable medication regimen (no change in dose or agents between 2 weeks prior to the start of and throughout the treatment phase of the study)
5) Implants or medical devices incompatible with TMS	5) Stable social environment and housing to enable regular attendance at clinic visits
6) Acute or unstable chronic medical illness that would affect participation or compliance with study procedures, e.g. unstable angina	6) Stable medical health
 Unstable psychiatric symptoms that precludes consistent participation in the study, e.g. active current suicidal intent, or plan; severe psychosis 	
8) Other substance use disorder not in remission	
9) Chronic or recurring Axis I psychotic disorders	
10) For subjects participating in fMRI scans in Aim 3, presence of ferromagnetic material in their body or taking DAergic medications	

Table 2. Inclusion and Exclusion Criteria

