Time window of last stimulant use at study entry. Subjects will be recruited whose last use of stimulants is greater than 2 weeks but less than 8 weeks. The former will ensure that study participation occurs after subjects fully complete stimulant detoxification and withdrawal, which may preclude reliable participation in the study and confound hypothesis testing. The upper limit of 8 weeks is intended to maximize the likelihood of detecting a treatment effect. It is clear from the investigators' clinical experience that the first eight weeks following drug use cessation includes the highest risk period for relapse, and therefore, is also the period for a treatment to have the greatest impact on lowering relapse rates. The date of last use will be ascertained using the Timeline Followback (TLFB) method described below.

Screening procedures

Initial telephone interview. Potential participants identified by clinical staff will be given a brief description of study procedures and research goals. Interested subjects will provide verbal consent to be contacted by research staff, who will conduct a telephone screen to determine initial study eligibility as well as to provide basic study information. Subjects passing the telephone screen and providing written consent for study participation will proceed to an in-person clinical assessment. Table 2 summarizes the inclusion and exclusion criteria for this study.

Discussion of inclusion/exclusion issues. The inclusion/exclusion criteria have been derived based on two principles: safety vis-à-vis experimental procedures (rTMS), and limiting major confound.

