rTMS and seizures. Although the actual incidence of seizure during rTMS is thought to be "very low" (Rossi et al., 2021), with estimates of 0.31 per 10,000 sessions and 0.71 per 1000 patients (Taylor et al., 2021), seizures, nonetheless remains the single most significant safety concern. This concern is particularly relevant for a study of users of stimulants since these agents are well known to lower seizure threshold. However, a review of the literature shows that high frequency rTMS has been well-tolerated in rTMS treatment studies of SUD. In the several publications involving over 100 subjects with SUD, no cases of seizures or any other significant adverse events have been reported (Bolloni et al., 2016; Camprodon et al., 2007; Politi et al., 2008; Rapinesi et al., 2016; Su et al., 2017; Terraneo et al., 2016). Nonetheless, we will institute procedures to minimize the possibility of seizures in our subjects. These procedures can be found in the Human Subjects section. These include administering a urine toxicology test just prior to the start of treatment and at least one additional test at a randomly chosen time point during the treatment phase. Most antipsychotics and antidepressants are thought to lower seizure threshold (Bolloni et al., 2016; Camprodon et al., 2007; Politi et al., 2008; Rapinesi et al., 2016; Su et al., 2017; Terraneo et al., 2016) prompting questions about the safety of administering rTMS to individuals taking these medications. However, the best available evidence suggests that these agents likely do not significantly increase the risk of rTMSinduced seizures. A review of various psychoactive agents, including antidepressants and antipsychotics (Ziemann, 2004), revealed that these agents in general do not affect motor threshold, which can be taken as a proxy measure for an agent's effect on cortical excitability, and hence a mediator of seizure potential. However, due to the particularly higher seizure risks associated with clozapine, chlorpromazine, and clomipramine (Pisani et al., 2002), as well as with high dose of bupropion (>400mg/day), we will exclude subjects taking these agents.

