Functional status. To quantify the functional impact of SUD and changes resulting from treatment, we will utilize the Addiction Severity Index (ASI). It is an instrument specifically developed to assesses the impact of substance use disorders on several domains of function, including medical, employment/support status, legal, family/social, and psychological. It is one of the best validated and commonly used scale for research into the problems associated with substance abuse (Amin-Esmaeili et al., 2024; McLellan et al., 2010; Miguel et al., 2021). Consequently, the ASI will facilitate the integration and comparison of results from this proposal to findings in the literature. To supplement this measure, we will also apply the Community Integration Questionnaire (CIQ) (Dijkers, 1997) as an additional measure of functional change. The CIQ will complement the ASI since it is broader and more general assessment of everyday functioning in the community. Both assessments will be administered two times: pre-treatment and 3 months after completion of the last treatment session.

Randomization of subject treatment assignments, drop-outs and subject flow. We will use a modification of the Efron procedure (Efron, 1971) developed by [name] (H. Kraemer, C., 1981) to randomize

participants and to assure comparable stimulant use severity between groups at baseline. Subjects screened out during baseline (prior to randomization) will be replaced. After randomization, dropouts will not be replaced but will be retained in the statistical modeling, i.e. their data will be retained in these analyses because they are equivalent to intention to treat analyses. This minimizes loss of power and bias caused by dropouts.

Treatment Phase

rTMS stimulation parameters

2.a.3.d. Post-Treatment Phase

2.a.3.d.1. Assessment of relapse

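### Allocation is drawn before the baseline scan and, most naturally, before the pre-treatment urine test, so anyone lost in that gap stays in the ITT comparison untreated, at a modest and avoidable cost in power

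*Protocol*

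**What the plan says.** Table 1 (Outline of Design) runs: clinical assessment, randomisation, baseline (fMRI), treatment, post-treatment. It carries an end-of-week-1 label ahead of treatment in weeks 2-4. The Overview of General Design gives a compatible order: "After pre-treatment assessment to confirm SUD diagnosis and characterize baseline level of use and functioning, subjects will be randomized", and then "They will then receive rTMS or sham in the 2-week treatment phase".

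For the last-use window (more than 2 and less than 8 weeks at study entry), the protocol says: "The date of last use will be ascertained using the Timeline Followback (TLFB) method described below". This is a self-report method. The only objective check of use that the supplied text describes before treatment is in the paragraph on rTMS and seizures: "administering a urine toxicology test just prior to the start of treatment". Its stated purpose there is safety: "we will institute procedures to minimize the possibility of seizures in our subjects". For details the reader is sent elsewhere: "These procedures can be found in the Human Subjects section". That section is not in the supplied text.

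The paragraph on randomisation, drop-outs and subject flow sets the replacement rule: "Subjects screened out during baseline (prior to randomization) will be replaced. After randomization, dropouts will not be replaced", and those dropouts are kept in the modelling. The SAP makes ITT the analysis for hypothesis testing. It adds a per-protocol analysis of people who completed all treatments and an examination of dropout.

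**The concern.** The moment of allocation decides which side of the replacement rule a person falls on. Before it, a lost participant is replaced; after it, they are a permanent ITT member. The plan draws the allocation with at least one study step (the scan) and probably a second (the urine test) still to come before the first session. It does so in people whom the protocol itself places in the period of highest relapse risk.

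Anyone who withdraws or does not start in that gap contributes an outcome that the assigned treatment cannot have affected, and this pulls the two arms together. The way such a person is counted is also unclear. The primary outcome window starts at treatment completion, a date that does not exist for someone never treated.

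**Working it through.** **No plan figure to reproduce.** The supplied documents give no sample size, power, alpha, relapse rate, dropout rate or gap length. Everything numerical below is illustration on stated assumptions.

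**Step 1: the order of events.**
- Allocation precedes the baseline scan (Table 1).
- The urine test is tied to the start of treatment (rTMS and seizures paragraph). Table 1 does not show the test, so its place after allocation is an inference, though the natural one.
- The medication-stability criterion in Table 2 is also counted from the start of treatment, so it too is still open when allocation is drawn.

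**Step 2: the gap.** From the end of week 1 to the start of week 2 is nominally a few days or less. Weeks 2-4 span three weeks while the text describes a two-week phase. A course could therefore start up to 3 - 2 = 1 week later and still fit. Gaps of 1, 3 and 7 days are used.

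**Step 3: the dilution.** Let a share f of each arm go untreated, with the same relapse risk q in both arms. With sham risk p0 and active risk p1:

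ITT difference = [(1-f)p0 + fq] - [(1-f)p1 + fq] = (1-f)(p0 - p1)

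The required sample grows by roughly 1/(1-f)², so the equivalent loss of sample is 1 - (1-f)².

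**Step 4: a range for f.** Assume a constant hazard over 13 weeks, a three-month sham relapse of 50%, 60% or 70%, and that every person who relapses in the gap goes untreated:

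h = -ln(1 - p0)/13 per week; f = 1 - exp(-h × days/7)

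| Gap | f at 50% | f at 60% | f at 70% | Equivalent sample loss (50% to 70%) |
|---|---|---|---|---|
| 1 day | 0.8% | 1.0% | 1.3% | 1 - 0.992² = 1.6% to 1 - 0.987² = 2.6% |
| 3 days | 2.3% | 3.0% | 3.9% | 1 - 0.977² = 4.5% to 1 - 0.961² = 7.6% |
| 7 days | 5.2% | 6.8% | 8.8% | 1 - 0.948² = 10.1% to 1 - 0.912² = 16.8% |

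**Step 5: what that does to power.** Assume 60% sham against 40% active, two-sided 5% and 1:1 allocation. With f = 0, 97 per arm give 80% power.

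| f | ITT difference | Power at 97 per arm | n per arm for 80% |
|---|---|---|---|
| 1% | 19.8 points | about 79% | 99 |
| 3% | 19.4 points | about 78% | 103-104 |
| 7% | 18.6 points | about 74% | 112-113 |

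The ranges in the last column cover q = 60% and q = 100%. Results for 50% against 30% and 70% against 50% are similar.

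**Step 6: which way these figures err.** They are high in assuming that every gap relapser goes untreated. They are low in leaving out people who withdraw before the first session for other reasons.

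**The case against.** The strongest reply is that this is ITT doing its job. Keeping people who never start is the purpose of the analysis, and under blinding the loss should be the same in both arms. The SAP already adds a per-protocol analysis and a check on dropout. The nominal gap is a few days at most, so the cost is small. All of that stands. It limits the point to power and to a modest size, but it does not explain why allocation should come before steps that could precede it at little cost.

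Four stronger readings are tempting, and the documents do not support them.

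- *A reader might infer that the replacement rule contradicts Table 1.* It need not. Being screened out at baseline fits the clinical assessment, which both the overview and Table 1 put before randomisation. The table's baseline column holds only the scan. One word has two uses, and the order is consistent.
- *A reader might infer that a positive urine test makes a person ineligible.* The protocol presents the test as a seizure precaution and gives no consequence in the supplied text. The last-use window is stated at study entry. If people with a positive test are still treated, dilution by untreated people does not follow for them.
- *A reader might infer that the scan is an eligibility gate.* The only scan-related exclusion is limited: "For subjects participating in fMRI scans in Aim 3, presence of ferromagnetic material in their body or taking DAergic medications". Nothing says that a missed scan ends treatment.
- *A reader might assume that 5-15% are lost in the gap*, a loss of 10-28% of the sample by the same formula. The documents give no basis for that range. A gap of a few days implies about 1-4% from new relapse on the assumptions above, and 15% lies beyond even the one-week case.

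**Conclusion.** The point holds in a narrow form. Table 1 draws the allocation earlier than it needs to. Because later losses are neither replaced nor removed, people lost before the first session dilute the primary comparison by the factor 1-f. On the stated assumptions the cost is equivalent to about 2-8% of the sample for a gap of 1-3 days and 10-17% for a week. In the 60% against 40% illustration, power falls from 80% to about 78-79% and about 74% respectively.

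The conclusion rests on three things the documents leave open: the length of the gap, the share who do not start, and the position of the urine test relative to allocation. The loss is expected to be non-differential, so the validity of the test is not in question. It is worth acting on because the remedy is cheap, not because the damage is large.

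**What to change.** Draw the computer allocation on the day of the first session, after the baseline fMRI (for those scanned) and after the urine test already planned, and re-order Table 1 to match. People who withdraw before that moment then fall under the existing pre-randomisation replacement rule. This moves only the time of allocation; no clinical rule for a positive test is proposed.

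The sponsor should also:
- reconcile the pre-treatment urine test with the last-use criterion in Table 2 and the time-window paragraph, so that the relation between the two is stated;
- reconcile weeks 2-4 in Table 1 with the two-week treatment phase in the overview, since this sets the gap;
- state in the SAP how a person randomised but never treated is counted for the primary outcome, because the window has no start date for them. If enrolment is too advanced to move the allocation, this is the part that still matters.

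The cost is an edit to Table 1 and to the randomisation procedure. Allocation must be available on the day of the first session, and some baseline scans will be spent on people who are never randomised.

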Psychotropic medications. We will document all psychoactive medications taken by our subjects during study participation so that we can conduct post-hoc moderator analysis of their impact on treatment efficacy. For subjects participating in Aim 3, we will exclude veterans taking DAergic medications, such as bupropion. This is because DA is well known to strongly modulate reward processing in subcortical circuits of interest in this study. Hence, DAergic medications are likely to confound measurements of reward associated activity. A review of our pilot study indicates that this exclusion criteria would affect ~10% of subjects.

Pre-treatment, in-person assessment

Diagnostic assessment. Inclusion and exclusion criteria, outlined in Table 2, will be reviewed in person. A doctoral or a master level clinician trained to administer the Structured Clinical Interview for DSM-5 Axis I Disorders (SCID) will conduct interviews to confirm the diagnosis of SUD, severe, and the presence of psychiatric co-morbidity.

Severity of stimulant use. The quantification of stimulant use with a common metric is notoriously difficult due to the wide variability in purity and content of stimulants across samples, diversity in method of administration and street value/cost between communities. Consequently, the number of days of use within a time window may be the most reliable and straightforward quantification method for stimulant use. We will use the Timeline Followback (TLFB) method for this purpose (https://www.nova.edu/timeline/index.html). This method has been demonstrated to be highly reliable with a variety of substances of abuse, including stimulants (Robinson et al., 2014). We will quantify the number of days of use within a 60-day period prior to the start of the relapse period in which participation occurred. We will conduct exploratory analyses with this information to investigate the possibility that severity of stimulant use moderates rTMS treatment effects. We will also estimate use severity of other substances with the using the TLFB to explore the possibility that use of other substances moderates rTMS treatment effects.

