The primary outcome measure will be rate of relapse within a three-month period following rTMS treatment completion. Relapse within the 3-month period following treatment will be determined using the Timeline Followback (TLFB) method. Subjects will be contacted monthly to review the prior months use history if any. We will supplement this assessment with a review of electronic medical records to look for evidence of relapse, such as progress notes from clinical staff and urine toxicology results. Relapse is defined as any use of a stimulant. Frequent testing occurs for veterans enrolled in ATS at the Palo Alto VA Medical Center, where most subjects will be recruited and will continue to be seen in their treatment programs.

Secondary outcome measures will be: 1) duration of sobriety following end of treatment phase; 2) change in level of craving (assessed by 10-point Likert scale) at end of treatment phase and three month follow up compared to baseline; 3) amount of stimulant use quantified as number of days of use of stimulants normalized by baseline values.

References

Ashok, A. H., Mizuno, Y., Volkow, N. D., & Howes, O. D. (2017). Association of Stimulant Use With Dopaminergic Alterations in Users of Cocaine, Amphetamine, or Methamphetamine: A Systematic Review and Meta-analysis. *JAMA Psychiatry*, *74*(5), 511-519.

Bohnert, K. M., Ilgen, M. A., Louzon, S., McCarthy, J. F., & Katz, I. R. (2017). Substance use disorders and the risk of suicide mortality among men and women in the US Veterans Health Administration. *Addiction*, *112*(7), 1193-1201.

Camprodon, J. A., Martinez-Raga, J., Alonso-Alonso, M., Shih, M. C., & Pascual-Leone, A. (2007). One session of high frequency repetitive transcranial magnetic stimulation (rTMS) to the right prefrontal cortex transiently reduces cocaine craving. *Drug Alcohol Depend*, *86*(1), 91-94.

Cho, S. S., & Strafella, A. P. (2009). rTMS of the left dorsolateral prefrontal cortex modulates dopamine release in the ipsilateral anterior cingulate cortex and orbitofrontal cortex. *PLoS One*, *4*(8), e6725.

Cox, K. B., Malte, C. A., & Saxon, A. J. (2017). Characteristics and Service Utilization of Homeless Veterans Entering VA Substance Use Treatment Psychological Services *Psychological Services*, *14*(2), 208-213.

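### The ITT chi-square on 3-month relapse has no rule for participants whose status is unknown and no analysis of how far the result depends on them; the SAP's data-triggered covariate step does not fill the gap

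*Protocol*

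**What the plan says.** **Outcome.** The Protocol (Assessment of relapse) sets the primary outcome as "rate of relapse within a three-month period following rTMS treatment completion", and "Relapse is defined as any use of a stimulant". Status comes from monthly TLFB contacts. Charts are a second source: "We will supplement this assessment with a review of electronic medical records to look for evidence of relapse". On how complete they are, the Protocol says: "Frequent testing occurs for veterans enrolled in ATS at the Palo Alto VA Medical Center", where most but not all subjects will be recruited.

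**Dropouts.** The Protocol (Randomization of subject treatment assignments, drop-outs and subject flow) says "dropouts will not be replaced but will be retained in the statistical modeling", equates this with intention to treat, and adds: "This minimizes loss of power and bias caused by dropouts".

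**Analysis.** The SAP (Hypothesis Testing) compares relapse rates by chi-square under intention to treat, with a supplementary per-protocol analysis of those who completed every rTMS session. It will check for greater dropout in the treatment group, compare dropouts with non-dropouts, and correct significant differences with covariates in unspecified models. Regression is named in the next paragraph, for baseline imbalance between arms, and only if imbalance is found.

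**Baseline severity.** It is measured as "the number of days of use within a 60-day period", and the adaptive randomisation uses it "to assure comparable stimulant use severity between groups at baseline".

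**The concern.** Any documented use settles a participant as relapsed. The open case is the person abstinent at last contact with no later TLFB or chart entry. That person cannot enter a 2x2 table until someone assigns a status, and the plan does not say which. Relapse is a plausible reason to stop answering monthly calls, so the unknowns may not resemble the rest.

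Two groups need separating. For people who stop treatment but are still followed, retention does limit bias, as the Protocol says. For people whose outcome is unknown, retention alone does nothing.

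The other planned analyses do not help. The per-protocol set selects on treatment completion, not on known outcome. The covariate step depends on which differences reach significance, and baseline covariates cannot account for loss driven by relapse beyond what they predict. A borderline primary result could then rest on a coding choice made after the data are seen.

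**Working it through.** The documents give no sample size, alpha, relapse rate or loss rate, so there is no planned figure to reproduce. Every input below is an assumption: 1:1 allocation, 50 per arm, two-sided 5%, Pearson chi-square without continuity correction.

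**1. Can the coding choice decide the result?**

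Known relapse is 12/40 active and 22/42 sham, with 10 and 8 unknown. The statistic is X² = (p₁ − p₂)² / [p(1 − p)(1/n₁ + 1/n₂)], where p is the pooled proportion.

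| Rule | Active | Sham | X² | p |
|---|---|---|---|---|
| Known only | 12/40 | 22/42 | 4.23 | 0.040 |
| Unknown = abstinent | 12/50 | 22/50 | 0.04/(0.34 × 0.66 × 0.04) = 4.46 | 0.035 |
| Unknown = relapsed | 22/50 | 30/50 | 0.0256/(0.52 × 0.48 × 0.04) = 2.56 | 0.109 |

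The SAP's check of dropout by arm, 10/50 against 8/50, gives X² = 0.0016/(0.18 × 0.82 × 0.04) = 0.27, p = 0.60. It would raise no flag.

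Let i of the 10 active unknowns and j of the 8 sham unknowns have relapsed. There are 11 × 9 = 99 combinations. p is below 0.05 in 45 of them, exactly those with i ≤ j (1 + 2 + … + 9 = 45). At the edges, i = 0, j = 0 gives 0.035 and i = 1, j = 0 gives 0.059; i = 8, j = 8 gives 0.046 and i = 9, j = 8 gives 0.072.

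**2. When is the test biased?**

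Assume no true effect, 50% relapse in both arms, all lost participants relapsed, and records documenting half of the lost relapsers. With loss fraction L, the documented half leaves L/2 unknown. Expected relapse is (0.5 − L/2)/(1 − L/2) on known outcomes and 0.5 − L/2 if unknowns count as abstinent.

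| Loss, active vs sham | Known only | Unknown = abstinent |
|---|---|---|
| 15% vs 15% | equal | equal |
| 20% vs 15% | 0.400/0.900 = 44.4% vs 0.425/0.925 = 45.9% | 40.0% vs 42.5% |
| 25% vs 10% | 0.375/0.875 = 42.9% vs 0.450/0.950 = 47.4% | 37.5% vs 45.0% |

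Simulated false-positive rates (400,000 trials per setting; 80–100% of the lost relapsed; half of lost relapsers documented, except that the equal-loss row covers none or half):

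| Loss | Known only | Unknown = abstinent |
|---|---|---|
| 15% vs 15% | 5.1–5.2% | 5.0–5.5% |
| 20% vs 15% | 5.2–5.5% | 6.0–6.3% |
| 25% vs 10% | 5.4–7.3% | 10.0–12.4% |

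No single rule is safe. At 25% vs 10%, counting unknowns as relapsed gives 5.6–6.7% if 80–100% of the lost relapsed, but 12.4% if only half did.

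**3. Does covariate adjustment repair it?**

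Take a separate no-effect case in which sham loses 20% of relapsers and active 40%, each arm loses 10% of abstainers, and nothing is documented. Expected known-outcome relapse is 0.40/0.85 = 47.1% in sham and 0.30/0.75 = 40.0% in active. In 3,000 simulated trials of 50 per arm, false positives are 11.4% unadjusted and 10.2% after adjusting for a prognostic baseline covariate; the mean odds ratio is 0.73 and 0.72 (truth 1). Adjustment leaves the bias. In fairness, in a similar simulation where loss depended only on arm and the covariate, adjustment worked (4.6% false positives, median odds ratio 1.01).

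**The case against.** **The covariates are not meant for the chi-square.** A reader might infer that the dropout correction is impossible because a chi-square takes no covariates. The SAP does not support that reading: it places the covariates in its statistical models and names regression in the next paragraph. What stands is that no model is specified for dropout and that significance decides whether it is used.

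**The window is not wholly undefined.** A reader might infer that someone who stops rTMS early has no 3-month window at all. Table 1 shows monthly relapse status over weeks 5–16 for both arms, and the secondary outcomes count from the end of the treatment phase. Candidate starting points exist. What stands is that they differ and must be reconciled for early stoppers.

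**Charts will fill many gaps.** Most subjects will come from a programme with frequent testing and stay in it. This narrows the gap. It does not close it: the review looks for evidence of relapse, and nothing says that an empty chart means abstinence.

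**The arms are blinded and the inputs are invented.** Both points stand. Nothing in the documents predicts unequal loss. If none of the lost relapsers were documented, 25% vs 10% loss could give false-positive rates as high as 35.8%; the chart review and testing make that extreme a poor guide. The worked example was chosen to be borderline.

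**Conclusion.** The omission is real and needs no assumed number: no status rule for unknowns and no analysis of how much they matter. Its consequence is conditional. In a borderline trial with a fifth or fewer unknown per arm, the rule can decide significance (0.035 to 0.109 in the example). Equal loss does not inflate the test. Mildly unequal loss with half of lost relapsers documented leaves a known-outcomes analysis near nominal (5.2–5.5%); markedly unequal loss gives 5.4–7.3%, or 10.0–12.4% if unknowns count as abstinent.

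A reader might infer that the planned test is biased, or that its error rate is badly inflated. The documents do not support that, because they give neither the size of loss nor any sign that it differs by arm. This should be fixed; it does not invalidate the design.

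**What to change.** Before unblinding, amend the SAP as follows.

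- **(a) One fixed model.** Replace both the significance-triggered dropout correction and the imbalance-triggered regression with one prespecified logistic model containing arm and baseline stimulant use severity (days of use in 60 days). Severity is already collected and already balanced by the randomisation. Use the same participants and status rule as the chi-square. This removes data-driven covariate choice; it does not correct relapse-related loss.
- **(b) A tipping-point table.** Report unknowns by arm. Vary relapse among them from none to all in each arm separately, and mark where the conclusion changes. This is the part that addresses relapse-related loss, whichever rule is chosen.
- **(c) One status rule and one window.** State what TLFB or chart information makes a status known, and one rule for the rest, identical in both arms. The choice is the sponsor's (for example known outcomes only with its assumption stated, imputation within arm, or unknown counted as relapsed). It should not assume frequent testing for everyone. Reconcile the window starting points so that randomised participants who stop early have a defined 3-month period.

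The cost is SAP wording, one model and one table. Monthly contacts and chart review are already planned. The downside is a little more analysis and possibly a less firm conclusion.
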